4.4.2 Data Collection and Follow-up for Withdrawn Subjects

At the time of withdrawal, the reason for withdrawal will be recorded in the CRF. Individuals who withdraw will go into the observation phase for 4 weeks. If a subject withdraws consent, attempts will be made to obtain permissions to collect follow up information.

5 Study Drug

5.1 Description (Investigator's Brochure)

The chemical name of Baricitinib (LY3009104) is $2-(3-(4-(7H-pyrrolo[2,3-d]pyrimidin-4-yl)-1H-pyrazol-1-yl)-1-(ethylsulfonyl)azetidin-3-yl)acetonitrile (Figure 1). Baricitinib (LY3009104) has a molecular formula of <math>C_{16}H_{17}N_7O_2S$ and a molecular weight of 371.42.

Baricitinib (LY3009104) Structural Formula

Baricitinib (LY3009104) drug substance is a white to practically white to light pink powder. Baricitinib (LY3009104) has been formulated in 3 strengths (1 mg, 2 mg, or 4 mg) that are actively being investigated.

Baricitinib (LY3009104) is an oral formulation of an investigational product under development for the treatment of patients with rheumatoid arthritis, alopecia areata, atopic dermatitis, psoriasis, systemic lupus erythematosus and other potential autoimmune diseases of the skin. Baricitinib (LY3009104) is an oral selective inhibitor of the Janus kinase (JAK) family of protein tyrosine kinases with selectivity for JAK1 and JAK2, and less selectivity for JAK3 with potent activity on the cytokine IFN-γ. JAK1 and JAK2 mediate the signaling of a number of cytokines and growth factors that are important for hematopoiesis and immune function. JAK signaling involves recruitment of STATs (signal transducers and activators of transcription) to cytokine receptors, activation and subsequent localization of STATs to the nucleus leading to modulation of gene expression. Mitogenic and inflammatory cytokines are strongly implicated in the pathogenesis of psoriasis, alopecia areata, atopic dermatitis, and other potential autoimmune diseases of the skin. Inhibition of specific cytokine function using antibodies directed against the common p40 subunit of interleukin (IL)-12 and IL-23 has demonstrated proof-of-concept validating cytokine signaling as a therapeutic target for the treatment of psoriasis.

Pharmacodynamics:

The decrease in the cytokine-stimulated pSTAT3 formation in response to single- and multiple dose baricitinib was measured in 3 clinical pharmacology studies. Data showed a dose dependent inhibition of pSTAT3 formation in response to cytokine stimulation in the single dose range of 1-mg to 20-mg (Study JADF) and multiple once-daily doses of 2-mg to 20-mg for

10 days (Study JADE). Similar levels of inhibition were observed using either IL-6 or TPO as

the stimulus. Maximal inhibition of pSTAT3 formation occurred approximately 1 to 2 hours post-dose, coincident with t_{max}. The pSTAT3 levels returned approximately to baseline levels by 24 hours for all dose groups following single and multiple doses. Based on the results from Study JADF and Study JADE, a PK/PD relationship was established for baricitinib-induced inhibition of IL-6 stimulated pSTAT3 formation. The calculated IC50 value was 75 nM (27.9 ng/mL) from Study JADF and 100 nM (37.1 ng/mL) from Study JADE (for a combined value of 90 nM (33.3ng/mL). These results are similar to the IC50 value of 104 nM (38.6 ng/mL) estimated from in vitro data. These data suggest that QD dosing of 4-mg, but not 2-mg, results in a period of time when the baricitinib concentration in the central compartment is above the ex vivo IC50 for IL-6-stimulated pSTAT3 formation.

Pharmacokinetics:

Baricitinib is rapidly absorbed with a median time of maximum observed drug concentration (tmax) of 1 hour (range: 0.5 to 3 hours). Over a single-dose range of 1 mg to 30 mg in healthy subjects, mean estimates of baricitinib Cmax and AUC_(0-∞) increased approximately proportionally to dose. Baricitinib PK after multiple doses were predictable from single dose data. Accumulation during QD dosing was minimal, with an accumulation ratio of 1.11- and 1.15-fold for Cmax and AUC, respectively. Steady state was typically reached between the second and third doses.

Renal elimination of parent is the principal clearance mechanism for baricitinib, and baricitinib apparent clearance (CL/F) is directly related to baseline glomerular filtration rate (GFR). The differences in CL/F between populations are likely due to differences in renal function, which affects apparent renal clearance (CLr/F). Pharmacokinetic parameter estimates are also available for patients with atopic dermatitis based on Phase 2 Study I4V-MC-JAHG (JAHG), although a different PK model was applied. The estimated values of CL/F and apparent total volume of distribution were 12.3 L/h and 105 L, respectively for this patient population.

The mean absolute bioavailability of baricitinib was 79%. The protein binding of baricitinib was $50 \pm 2\%$ in plasma and $55 \pm 3\%$ in serum. Mean volume of distribution following IV administration was 75.7 L (21% coefficient of variation [CV]), suggesting distribution of baricitinib into tissues. About 75% of the baricitinib dose is excreted in the urine predominately as parent, and about 20% of the dose is excreted in the feces.

Bioequivalence was demonstrated between the baricitinib 4-mg commercial oral tablet and a 4-mg dose (2 mL of 2 mg/mL suspension) of a pediatric suspension in Study I4V-MC-JAGU. There was no statistically significant difference in exposure to baricitinib based on AUC and C_{max} between the tablet and suspension formulation when administered in the fasted state. When the suspension was administered with a high-fat, high-calorie meal, the C_{max} of baricitinib was reduced by 32.5% compared to the fasted state. The median t_{max} of baricitinib was also delayed by 2 hours in the fed compared to the fasted state; however, the overall exposure based on AUC was similar in the fed and fasted states.

Potential for Baricitinib (LY3009104) to Affect Other Drugs:

Cytochrome P450 Enzymes: In vitro, baricitinib did not significantly inhibit nor induce the activity of CYP enzymes (CYPs 3A, 1A2, 2B6, 2C8, 2C9, 2C19, and 2D6). In clinical pharmacology studies, coadministration of baricitinib with the CYP3A substrates simvastatin, ethinyl estradiol, or levonorgestrel resulted in no clinically meaningful changes to these drugs.

Transporters: In vitro, baricitinib did not inhibit the transporters Pgp or OATP 1B1. In vitro, baricitinib does inhibit OAT1, OAT2, OAT3, OCT1, OCT2, OATP1B3, BCRP, MATE1, and MATE2-K, but clinically meaningful changes to drugs that are substrates for these transporters are unlikely. In clinical pharmacology studies, there were no clinically meaningful effects when baricitinib was coadministered with digoxin (Pgp substrate) or MTX (substrate of several transporters).

Potential for Other Drugs to Affect Baricitinib:

Cytochrome P450 Enzymes: In vitro, baricitinib is a CYP3A4 substrate. In clinical pharmacology studies, coadministration of baricitinib with ketoconazole (CYP3A inhibitor) resulted in no clinically meaningful effect. Coadministration of baricitinib with fluconazole (CYP3A/CYP2C19/CYP2C9 inhibitor) or rifampin (CYP3A inducer) resulted in no clinically meaningful changes to baricitinib.

Transporters: In vitro, baricitinib is a substrate for OAT3, Pgp, BCRP, and MATE2-K. In a clinical pharmacology study, probenecid (OAT3 inhibitor with strong inhibition potential) dosing resulted in approximately a 2-fold increase in AUC(0-∞) with no change in Cmax of baricitinib. Simulations with diclofenac and ibuprofen (OAT3 inhibitors with less inhibition potential) predicted minimal effect on baricitinib. Coadministration of baricitinib with cyclosporine (Pgp/BCRP inhibitor) or MTX (substrate of several transporters) resulted in no clinically meaningful effects on baricitinib exposure.

5.2 Treatment Regimen

Subjects will administer Baricitinib (LY3009104) 2 mg tablet once daily on an empty stomach. Treatment will take place from Day 0 to Week 16.

5.3 Preparation and Administration of Study Drug

The study drug will be supplied by Eli Lilly to the Mayo Clinic Pharmacy, attn. [name], Pharm D, R.Ph. [name]. The study drug will be stored in the Mayo Clinic Pharmacy. The study drug will be labelled in the Mayo Clinic Pharmacy and will be dispensed to the subjects. The subjects will be given sufficient quantity of tablets at each visit for use between subsequent study visits. Instructions on proper use will be provided to each subject.

5.4 Subject Compliance Monitoring

Compliance will be assessed through direct questioning of subjects as well as through drug use diaries.

5.5 Prior and Concomitant Therapy

Individuals on stable doses of medications for chronic illnesses will be allowed. Individuals on immunosuppressive agents for LP will not be allowed; however, individuals on stable doses of immunosuppressant for other conditions will be allowed if deemed to be safe by the treating physicians. Additional exclusionary drugs are included in Table-1.

Individuals using Baricitinib (LY3009104) should use topical broad-spectrum sunscreens with a minimum of SPF30, avoid excess sunlight, and wear sun protective clothing.

5.6 Packaging

The drug will be packaged in bottles with 30 tablets of Baricitinib (LY3009104) 2 mg per bottle. The entire quantity needed for the study will be provided in one shipment. The study drug bottles will be labeled with a diaper label that fully surrounds the bottle. All applicable US FDA required text will be included on the label, included Caution: Limited by U.S. Law to Investigational Use.

5.7 Receiving, Storage, Dispensing and Return

5.7.1 Receipt of Drug Supplies

The drug will be obtained or delivered from Eli Lilly and Company to the pharmacy at each investigative site.

Upon receipt of the of the study treatment supplies, an inventory must be performed and a drug receipt log filled out by the person accepting the shipment. It is important that the designated study staff counts and verifies that the shipment contains all the items noted in the shipping invoice. Any discrepancies, damaged or unusable study drug in a given shipment (active drug or comparator) will be documented in the study files. The sponsor-investigator must be notified immediately of any discrepancies, damaged or unusable products that are received.

5.7.2 Storage

The Baricitinib (LY3009104) drug product should be stored between 15°C and 30°C (59°F and 86°F). The supplies will be stored in the Mayo Clinic Pharmacy.

5.7.3 Dispensing of Study Drug

Regular study drug reconciliation will be performed to document drug assigned, drug dispensed, drug returns, and drug remaining. This reconciliation will be logged on the drug reconciliation form and signed and dated by the study team. A three month extension and dose excalation to 4mg will be available to all patients who demonstrate response to treatment, but have not yet achieved PGA 0

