1.5 Dose Rationale

Balancing the safety risks and efficacy data of varying baricitinib doses from prior studies, our study proposes oral Baricitinib (LY3009104) 2 mg QD dosing for 16 weeks (primary endpoint) in LP study subjects. If the patient opts into the extension portion of the study, the dose will escalate to 4 mg.

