Individuals will then initiate treatment for all lesions of LP once daily and will be evaluated weekly and assessed by PGA of skin, oral mucosa, and hair, BSA, lesion count, Modified CAILS, Pruritus VRS, VAS and NRS scales, Skindex-16, and LPQOL between weeks 0-16 (see Appendix). Week 16 will be the primary endpoint. Therapy will be stopped and the individuals will be evaluated at week 20 after an observation period of 4 weeks and assessed by PGA, BSA, lesion count, mCAILS, Pruritus VRS, VAS and NRS scales, Skindex-16, and LPQOL. Laboratory and safety monitoring will occur at weeks 1, 2, 3, 4, 8, 12, 16, 20, 24, 28, and 32. 3D Photographs will be taken at weeks 0, 1, 2, 3, 4, 8, 12, 16, 20, 24, 28, and 32. Individual lesions will be circled at each visit and the exact area of each lesion will be measured. Up close photos will be taken of the disease.

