- Underlying condition (including, but not limited to metabolic, hematologic, renal, hepatic, pulmonary, neurologic, endocrine, cardiac, infectious or gastrointestinal conditions) which, in the opinion of the investigator, significantly immunocompromises the subject and/or places the subject at unacceptable risk for receiving an immunomodulatory therapy
- Moderate-to-severe renal impairment including patients with estimated glomerular filtration rate (eGFR) <60 mL/min/1.73m²
- Active systemic infections during the 2 weeks prior to randomization (common cold viruses excluded) or any infection that reoccurs on a regular basis.
- Current severe progressive or uncontrolled disease which the investigator renders the subject unsuitable for the trial or puts the subject at increased risk
- Have had any major surgery within 8 weeks prior to screening or will require major surgery during the study that, in the opinion of the investigator would pose an unacceptable risk to the patient.
- Have experienced any of the following within 12 weeks of screening: VTE (DVT/pulmonary embolism [PE]), myocardial infarction (MI), unstable ischemic heart disease, stroke, or New York Heart Association Stage III/IV heart failure.
- Have a history of recurrent (≥ 2) VTE (DVT/PE).
- Have a history of lymphoproliferative disease; have signs or symptoms suggestive of possible lymphoproliferative disease, including lymphadenopathy or splenomegaly; have active primary or recurrent malignant disease; or have been in remission from clinically significant malignancy for <5 years prior to randomization.
- Have had symptomatic herpes zoster infection within 12 weeks prior to randomization.
- Have a history of disseminated/complicated herpes zoster (for example, ophthalmic zoster or CNS involvement).
- ALT or AST >2 x upper limits of normal (ULN); alkaline phosphatase (ALP) ≥2 x ULN; total bilirubin ≥1.5 x ULN; hemoglobin <10 g/dL (100.0 g/L); total white blood cell count <3000 cells/μL (<3.00 x 103/μL or <3.00 billion/L); neutropenia (absolute neutrophil count [ANC] <1500 cells/□L) (<1.50 x 103/□L or <1.50 billion/L); lymphopenia (lymphocyte count <1000 cells/μL) (<1.00 x 103/μL or <1.00 billion/L); thrombocytopenia (platelets <100,000 cells/μL) (<100 x 103/μL or <100 billion/L)
- Have a positive test for hepatitis B virus (HBV) defined as:
 - a. positive for hepatitis B surface antigen (HBsAg), or

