Temporary Interruption of Investigational Product: In some circumstances, patients may need to temporarily interrupt treatment as a result of AEs or abnormal laboratory values that may have an unclear relationship to investigational product. For the abnormal laboratory findings and clinical events (regardless of relatedness), specific guidance is provided for temporarily interrupting treatment and when treatment may be restarted. Retest frequency and timing of follow up laboratory tests to monitor the abnormal finding is at the discretion of the investigator. Investigational product that was temporarily interrupted because of an AE or abnormal laboratory value may be restarted at the discretion of the investigator.

- Absolute Neutrophil Count (ANC): Treatment should be interrupted if ANC < 1 x 109 cells/L and may be restarted once ANC return above this value
- Absolute Lymphocyte Count (ALC): Treatment should be interrupted if ALC $< 0.5 \times 109 \text{ cells/L}$ and may be restarted once ALC return above this value
- Hemoglobin (Hb): Treatment should be interrupted if Hb < 8 g/dL and may be restarted once Hb return above this value
- Hepatic transaminases: Treatment should be temporarily interrupted if drug-induced liver injury is suspected

Permanent Discontinuation from Investigational Product: Investigational product must be permanently discontinued if the patient or the patient's designee requests to discontinue investigational product. Discontinuation of the investigational product for abnormal liver tests should be considered by the investigator when a patient meets 1 of the following conditions:

- ALT or AST >8 x ULN
- ALT or AST >5 x ULN for more than 2 weeks after temporary interruption of investigational product
- ALT or AST >3 x ULN and total bilirubin level (TBL) >2 x ULN or international normalized ratio (INR) >1.5
- ALT or AST >3 x ULN with the appearance of fatigue, nausea, vomiting, right upper quadrant pain or tenderness, fever, rash, and/or eosinophilia (>5%)
- ALP >3 x ULN that is deemed to be of liver origin and drug-related
- ALP >2.5 x ULN and TBL >2 x ULN
- ALP >2.5 x ULN with the appearance of fatigue, nausea, vomiting, right upper-quadrant pain or tenderness, fever, rash, and/or eosinophilia (>5%)
- Investigational product should be permanently discontinued if any of the following laboratory abnormalities are observed:

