Laboratory studies will be drawn as indicated in Table-2. Whether action needs to be taken to address notable laboratory values will be decided by the investigator, considering the overall status of the subject. Hematology assessments will be measured at all scheduled study visits specified in Table-2. Serum chemistry will be a comprehensive metabolic panel will be measured at all scheduled study visits specified in Table-2.

Hospitalization, Prolonged Hospitalization or Surgery

Any adverse event that results in hospitalization or prolonged hospitalization should be documented and reported as a serious adverse event unless specifically instructed otherwise in this protocol. Any condition responsible for surgery should be documented as an adverse event if the condition meets the criteria for an adverse event.

Neither the condition, hospitalization, prolonged hospitalization, nor surgery are reported as an adverse event in the following circumstances:

• Hospitalization or prolonged hospitalization for diagnostic or elective surgical procedures for a preexisting condition. Surgery should **not** be reported as an outcome of an adverse event if the purpose of the surgery was elective or diagnostic and the outcome was uneventful.

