The occurrence of adverse events will be sought by non-directive questioning of the patient at each visit during the study. Adverse events also may be detected when the patient volunteers them during or between visits or through physical examination, laboratory test, or other assessments. Please see Supplemental 3 for a detailed description of safety monitoring. Clinically significant abnormal laboratory values or test results will be identified through a review of values outside of normal ranges/clinically notable ranges, significant changes from baseline or the previous visit, or values which are non-typical in patient with underlying disease. Investigators have the responsibility for managing the safety of individual patient and identifying adverse events. Alert ranges for labs and other test abnormalities are included determined by the Mayo Clinic Arizona and Mayo Medical Laboratory. Adverse events will be recorded in the Adverse Events Case Report Form (CRF) under the signs, symptoms or diagnosis associated with them, and severity. All adverse events will be treated appropriately. Once an adverse event is detected, it should be followed until its resolution or until it is judged to be permanent, and assessment should be made at each visit (or more frequently, if necessary) of any changes in severity, the suspected relationship to the study drug, the interventions required to treat it, and the outcome (see Supplemental 3). Information about common side effects already known about the investigational drug can be found in the package insert. This information will be included in the patient informed consent and should be discussed with the patient during the study as needed. The investigator will also instruct each patient to report any new adverse event (beyond the protocol observation period) that the patient, or the patient's personal physician, believes might reasonably be related to study treatment. This information should be recorded in the investigator's source documents, however, if the AE meets the criteria of an SAE. To ensure patient safety, every SAE (see Supplemental 3 for definition), regardless of suspected causality, occurring after the patient has provided informed consent and after the patient begins taking study drug and until 30 days after the patient has stopped study participation will be recorded and reported to Incyte. Any SAEs experienced after this 30-day period should only be reported to Incyte if the investigator suspects a causal relationship to the study drug. All malignant neoplasms will be assessed as serious under "medically significant" if other seriousness criteria are not met. Medical and scientific judgment will be exercised in deciding whether other situations should be considered serious reactions, such as important medical events that might not be immediately life threatening or result in death or hospitalization but might jeopardize the patient or might require intervention to prevent one of the outcomes listed in SAE. Any suspected transmission via a medicinal product of an infectious agent is also considered a serious adverse reaction. All AEs (serious and non-serious) are captured and recorded, SAEs also require individual reporting (see Supplemental 3). To ensure patient safety, each pregnancy occurring while the patient is on study treatment must be reported to the sponsor-investigator within 24 hours of learning of its occurrence. The pregnancy should be followed up to determine outcome, including spontaneous or voluntary termination, details of the birth, and the presence or absence of any birth defects, congenital abnormalities, or maternal and/or newborn complications. Pregnancy follow-up should be recorded on the same form and should include an assessment of the possible relationship to the study treatment. Any SAE experienced during the pregnancy and unrelated to the pregnancy must be reported on a SAE form.

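### The step from 2 mg to 4 mg carries no renal condition, although an eGFR below 60 bars a patient from starting 2 mg

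*Combined protocol and SAP*

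**What the plan says.** **The step to 4 mg.** Three sections describe it. Section 1.5: "If the patient opts into the extension portion of the study, the dose will escalate to 4 mg". Section 3.3 offers a three-month extension at 4 mg to responders who have not reached PGA 0. Section 5.7.3: "A three month extension and dose excalation to 4mg will be available to all patients who demonstrate response to treatment", again short of PGA 0. The written conditions are therefore response, PGA 0 not reached, and the patient's choice.

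**Renal function at entry.** Section 4.2 excludes "Moderate-to-severe renal impairment including patients with estimated glomerular filtration rate (eGFR) <60" mL/min/1.73m². This is the only eGFR limit in the document.

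**Rules on treatment.** The interruption and discontinuation rules in section 8.1 are numeric for several laboratory values, for example "Treatment should be interrupted if Hb < 8 g/dL and may be restarted once Hb return above this value". They cover neutrophils, lymphocytes, white cells, hemoglobin, liver tests and HBV DNA. They do not mention eGFR or creatinine.

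**Monitoring.** Section 3.1: "Laboratory and safety monitoring will occur at weeks 1, 2, 3, 4, 8, 12, 16, 20, 24, 28, and 32". Table 3 schedules a comprehensive metabolic panel (CMP) at Week 16. Section 8.5: "Clinically significant abnormal laboratory values or test results will be identified through a review of values outside of normal ranges/clinically notable ranges", and also by comparison with baseline and the previous visit. On the response to such values, section 3.6 and Supplemental 3 say: "Whether action needs to be taken to address notable laboratory values will be decided by the investigator".

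**The concern.** The protocol treats eGFR below 60 as sufficient reason not to begin 2 mg, but has no matching rule for beginning twice that dose. A patient who entered above 60, fell below it on 2 mg, and responded short of PGA 0 meets every written condition for 4 mg. Because the drug leaves the body mainly through the kidney, a fall in eGFR and a doubled dose would be expected to multiply in their effect on exposure.

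What is at stake is the safety of an individual patient at the highest dose used in the trial. The primary endpoint is PGA of the skin at Week 16, assessed on 2 mg, so the efficacy result is not touched.

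**Working it through.** **1. Text comparison.** The plan states no figure for this point, so there is none to reproduce.

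| Decision | Written renal condition | Source |
|---|---|---|
| Start 2 mg | eGFR not below 60 | 4.2 |
| Interrupt or stop treatment | None; numeric limits for counts and liver tests, plus an HBV DNA rule | 8.1 |
| Step up to 4 mg | None | 1.5, 3.3, 5.7.3 |

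**2. Sequence at Week 16.** The visit list (Visit 9) has both a blood draw and dispensing. Section 3.6 requires blood to be drawn before study treatment is given. That fixes the order of draw and dose; it does not require the result to be seen before 4 mg is handed over.

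**3. Illustrative size.** Inputs from section 5.1: renal elimination is the principal clearance route; apparent clearance is related to baseline GFR; about 75% of the dose is excreted in urine; absolute bioavailability is 79%; exposure is approximately proportional to dose.

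Assumptions that are not in the documents: clearance is linear in eGFR; the reference eGFR is 90; the relation to baseline GFR, which concerns differences between people, also holds for change within a patient.

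The renal share of clearance, f, is taken from 0.75 (urinary share of the oral dose) to 0.75/0.79 = 0.949 (share of the absorbed dose).

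- Relative clearance at eGFR g: CL(g) = (1 − f) + f × g/90
- Added exposure from a fall: CL(60)/CL(g)
- Dose step at any fixed eGFR: 4/2 = 2.0, because CL cancels

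| | f = 0.75 | f = 0.949 |
|---|---|---|
| CL(60) | 0.750 | 0.684 |
| CL(45) | 0.625 | 0.525 |
| CL(30) | 0.500 | 0.367 |
| CL(60)/CL(45) | 1.20 | 1.30 |
| CL(60)/CL(30) | 1.50 | 1.86 |

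Closer to the limit the factor is small: 1.01 to 1.02 at eGFR 59, and 1.125 to 1.18 at eGFR 50.

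**4. Sensitivity.** With a reference eGFR of 120, the added exposure is 1.18 to 1.29-fold at eGFR 45 and 1.43 to 1.82-fold at eGFR 30, so the choice of reference matters little.

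**The case against.** **Safeguards exist.** Section 3.6 and the Table 1 footnote say a subject at undue safety risk should stop treatment at the investigator's discretion. Section 8.1 allows interruption for abnormal laboratory values in general, before naming its limits. Clinically significant abnormalities are adverse events, and the listed actions include dose adjustment and discontinuation. The metabolic panel is scheduled seven times from Week 1 to Week 16. Section 8.5 also calls for a site safety-monitoring plan, which is not among the documents and might contain a check. All this stands: a reader might infer that renal function goes unwatched, or that escalation would be automatic, and the documents support neither. But these safeguards have no renal threshold, and none is made a condition of escalation. For blood counts and liver tests the protocol did not rely on discretion alone.

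**On-treatment limits are looser than entry limits by design.** Neutrophils go from 1500 to 1000 cells/µL, lymphocytes from 1000 to 500 cells/µL, and hemoglobin from 10 to 8 g/dL. One can argue that 60 need not carry over. This has some force for continuing 2 mg. Moving to 4 mg is closer to a new start, at a higher dose, and the entry limit is the only renal figure the sponsor has set.

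**A single check at Week 16 is partial.** Falls before then, or later on 4 mg, stay under discretion. True; the check addresses the escalation decision only.

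**Tolerability.** A reader might infer from section 1.4 that 4 mg is clearly less well tolerated: interruption for adverse events in SLE was 20.2% against 6.7% at 2 mg, and discontinuation in atopic dermatitis 16% against 8%. The documents do not carry that weight. Placebo rates were 10.5% and 10%, and the atopic dermatitis figures are 6/38 and 3/37 and include washout. Other comparisons of 2 mg with 4 mg are flat: SAEs 1% and 1% in Phase 3 atopic dermatitis, SAEs 10.5% and 9.6% in SLE, TEAEs 50.0% and 47.2% in psoriasis. None of these data is broken down by eGFR.

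**Conclusion.** The gap holds on the text: the step to 4 mg has no renal condition, the only eGFR limit applies at entry, and nothing requires the Week 16 result to be seen before dispensing. This conclusion does not depend on the clearance model.

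The size is modest and conditional. Under the assumptions above, a fall from eGFR 60 adds 1.2 to 1.3-fold exposure at 45 and 1.5 to 1.9-fold at 30. That increase would already be present on 2 mg, and the dose step then doubles it. A reader might multiply through to 2.4 to 3.7-fold and attribute the whole to the missing rule. That would be wrong, because the 2.0-fold step is the intended design; only the remaining factor belongs to this point. The documents do not say how often eGFR falls on 2 mg, and give no reason to expect a fall to 30 within 16 weeks. The number affected among 12 may be zero.

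A matching platelet condition might also seem to follow, since platelets too have an entry limit and no on-treatment limit. Support for it is weak: section 1.6 lists raised platelets as the common effect, with only a general remark on suppressed blood-cell growth.

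This is a cheap improvement for patient safety. It has no effect on the Week 16 primary endpoint.

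**What to change.** In section 5.7.3, cross-referenced from 1.5 and 3.3, add that 4 mg may be dispensed only after the Week 16 metabolic panel has been reviewed and shows eGFR of at least 60 mL/min/1.73m². A responder who does not qualify follows the path already in section 3.1: treatment stops at Week 16, followed by four weeks of observation.

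The cost is protocol wording. The panel is already scheduled in Table 3 and the threshold is the sponsor's own. The downside is that dispensing may wait for the result, and slightly fewer patients may escalate.
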